Assessment will be performed at the following time points until progression/start of further treatment (tumor assessments after randomisation should be performed no more than 7 days prior to the scheduled tumor assessment date up to week 48 AND no more than 14 days prior to the scheduled tumor assessment date after week 48):

- At screening (within 28 days prior start of treatment):
- Every 8 weeks: during week 8 (49-56 days after randomisation), during week 16 (105-112 days after randomisation), during week 24 (161-168 days after randomisation), during week 32 (217-224 days after randomisation), during week 40 (273-280 days after randomisation), during week 48 (329-336 days after randomisation)
- Every 12 weeks after week 48 (e.g. during week 59-60 (406 – 420 days after randomisation), during week 71-72 (490 – 504 days after randomisation), etc.)

In the event of an interruption/delay to treatment, the tumor assessment schedule should not be changed. Patients who discontinue the trial for any reason other than imaging based progressive disease should have a tumour assessment (RECIST 1.1) performed at EOTV. Except in case of discontinuation from treatment due to imaging based progression, tumor assessment at EOTV is not necessary if the previous evaluation was done within 4 weeks of EOTV

Unscheduled scan based on the investigator's judgement is allowed and should also be documented in eCRF

16. Everolimus, if supplied by the sponsor, should be dispensed through IRT. The prescription of everolimus (if not supplied by the sponsor) and exemestane should be filled by pharmacy. Patient's screening, randomization, all drug dispensation visits and EOTV will be collected in the IRT system

17. Compliance check: on Day 1 of course 2, 3, 4, 5, etc. and at EOTV

18. For Course 2 only

19. Completion of the phase II part: Completion of the phase II part of the study should be recorded at FU (the last FU visit) when PD/death occurs, starting of new treatment, consent withdrawal or death

20. Collection of information on disease status and further therapies: information on progression, further anti-cancer treatment and death should be collected from patient's notes or by telephone contact with the patient. A formal study visit is not required

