5.1.2 Phase II

The primary endpoint for the Phase II part of the study is PFS based on investigator assessment.

PFS is defined as the time from randomisation until radiological tumour progression according to RECIST guideline (version 1.1) ([R09-0262](#)) or death from any cause, whichever occurs earlier.

Tumour assessments are planned to be performed at screening and then every 8 weeks after randomisation until week 48 and every 12 weeks thereafter. After amendment 3 of the CTP (see also [Section 4.2](#)), the imaging schedule has been made more flexible. However, it was decided to keep the initial planned schedule for the definition of time windows for censoring rules (see also [Section 6.7.2](#)).

Proprietary confidential information © 2018 Boehringer Ingelheim International GmbH or one or more of its affiliated companies

For each follow-up imaging timepoint an overall tumour response will be determined according to RECIST 1.1. The overall tumour response for each imaging timepoint will be selected from the following categories: Complete Response (CR); Partial Response (PR); Stable Disease (SD); Progressive Disease (PD); Non-CR/Non-PD; Not Evaluable (NE).

For details on the imaging process and RECIST 1.1 evaluation, see Sections 5.1.2 and 10.4 of the CTP.

Derivation of endpoint PFS

Derivations below are described in days. However, the endpoints below will be presented in months in the outputs produced for the CTR.

For patients with 'event' as an outcome for PFS: (according to RECIST version 1.1)

- PFS [days] = date of outcome - date of randomisation + 1.

For patients with 'censored' as an outcome for PFS: (according to RECIST version 1.1)

- PFS (censored) [days] = date of outcome - date of randomisation + 1.

The censoring rules for PFS (i.e. outcome and date of outcome) are given in Table 5.1.2: 1. Clinical disease progression will not be considered for determination of a PFS event, unless the outcome of the progression is death.

If patients would have their radiological examinations over a number of days, i.e. target lesions assessed on day x, non-target lesions assessed on day y and new lesion (if applicable) on day z, the following rules will be applied:

- If the overall response is PD, the earliest date of multiple assessments will be taken.

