- If the overall response is SD, Non-CR/Non-PD, PR, CR or NE, the latest of multiple assessment dates will be taken, i.e. in the case of SD, Non-CR/Non-PD, PR, CR, the latest of multiple dates will be used to censor the patients.

Imaging assessments for which NE is assigned as the overall response at an imaging time-point are considered to be missed assessments. Please note that NE does not indicate lack of progression.

Table 5.1.2: 1 Derivation rules for PFS

Situation	Outcome (event or censored)	Date of outcome
No baseline radiological assessment		
Patient with death on or before the second planned radiological assessment	Event	Date of death

Proprietary confidential information © 2018 Boehringer Ingelheim International GmbH or one or more of its affiliated companies

Table 5.1.2: 1 Derivation rules for PFS (cont.)

Situation	Outcome (event or censored)	Date of outcome
Patient without death or patient with death after second performed radiological assessment	Censored	Date of randomisation (or first treatment administration, in non-randomised trials)
Without post-baseline radiological assessments		
Vital status is unknown or patient is known to be alive	Censored	Date of randomisation (or first treatment administration, in non-randomised trials)
Death prior or on the second planned radiological assessment	Event	Date of death
Death beyond the second planned radiological assessment	Censored	Date of randomisation (or first treatment administration, in non-randomised trials)
With baseline and post-baseline radiological assessments BUT no other anti-cancer therapy		
Alive and not progressed, no more than one consecutively missed radiological assessments	Censored	Date of last radiological assessment
Alive and not progressed, two or more consecutively missed radiological assessments	Censored	Date of last radiological assessment prior to missed radiological assessments
Progressed, zero or one missed radiological assessment prior to progression	Event	Date of radiological assessment of progression

Proprietary confidential information © 2018 Boehringer Ingelheim International GmbH or one or more of its affiliated companies

Table 5.1.2: 1 Derivation rules for PFS (cont.)

Situation	Outcome (event or censored)	Date of outcome
Progressed, but two or more consecutively missed radiological assessments prior to progression	Censored	Date of last radiological assessment prior to missed assessment

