6.2 IMPORTANT PROTOCOL VIOLATIONS

No per protocol set (PPS) analysis will be performed for this study, hence, no patient will be excluded from the analyses (except those with missing informed consent or not adhering to age limit). However patients with potentially important protocol violations (IPVs) will be documented. The following list of potentially IPVs in Table 6.2: 1 will be used; note that this is a working list and may not be finalised until the final Blinded Report Planning Meeting (BRPM) or DBL meeting (but prior to DBL for the primary analysis). Potentially IPVs will be handled according to BI standards [\(6\)](#).

During the study conduct, protocol deviation should be monitored and guidance for improving / teaching the respective sites should be discussed during the study Medical Quality Review Meetings (MQRMs).

Table 6.2: 1 Important protocol violations

Category/ Code		Description	Requirements	Excluded from
A [1]		Entrance criteria not met		
	A1	Diagnosis of trial disease questionable	Inclusion criteria* IN 1 or IN 2 not met.	None

Proprietary confidential information © 2018 Boehringer Ingelheim International GmbH or one or more of its affiliated companies

Table 6.2 : 1 Important protocol violations (cont.)

Category/ Code	Description	Requirements	Excluded from
	A2	Prohibited baseline condition, diagnosis or treatment At least one of inclusion criteria* IN 4- 9 or IN 12 is not met or At least one of exclusion criteria* is met.	None
	A3	Laboratory result indicating inadequate organ function at screening	Inclusion criteria* IN 10 or IN 11 not met
	A4	Adequate archival tumour tissue not available	Inclusion criterion* IN 3 not met.
B [1]		Legal Criteria	
	B1	Informed consent not available / not done	Informed consent date missing or inclusion criterion* IN 13 not met
	B2	Informed consent too late	Informed consent date was after Screening Visit date
	B3	Age limit for patient inclusion not adhered to	Calculate age given the date of birth and date of informed consent. Patients must be ≥ 18 years old.
C		Trial medication and randomisation	
	C1 [2]	Time window violation for procedures performed at screening	Screening imaging earlier than 28 days to first drug intake; Safety labs, ECG performed earlier than 28 days to, or later than first drug intake; Timeframe > 4 days between randomisation and first drug intake

Proprietary confidential information © 2018 Boehringer Ingelheim International GmbH or one or more of its affiliated companies

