6.7.2 Time windows for every RECIST assessment

In order to identify whether consecutive imaging timepoints are missing for a given patient, a nominal time point [8, 16, 24, 32, 40, 48 weeks and every 12 weeks thereafter] will be assigned to each and every image. This is achieved by creating windows for every RECIST 1.1 assessment. The windows are defined in Table 6.7.2: 1 below. Day 1 corresponds to date of randomisation for the Phase II part (for the Phase Ib part it corresponds to the date of first drug intake of xentuzumab).

Table 6.7.2: 1 Nominal time-points and windows for imaging

Nominal time-point [weeks from start of therapy]	Due date of scans [days]	Window [days]
8	57	1 to =< 85
16	113	86 to =< 141
24	169	142 to =< 197
32	225	198 to =< 253
40	281	254 to =< 309
48	337	310 to =< 379

Proprietary confidential information © 2018 Boehringer Ingelheim International GmbH or one or more of its affiliated companies

Table 6.7.2: 1 Nominal time-points and windows for imaging (cont.)

Nominal time-point [weeks from start of therapy]	Due date of scans [days]	Window [days]
60	421	380 to =<463
72	505	463 to =<547
every 12 weeks interval	etc (1)	etc (1)

(1) Due date of scans = (nominal time point * 7) + 1. To calculate the lower bound of the window, use the middle point between the due date of the previous time point and the current due date + 1. To calculate the upper bound of the window, use the middle point between the due date of the next time point and the current due date.

If a patient does not have an image in one of the windows described above, she will be said to have 'missed an assessment' for that timepoint. In case a patient has more than one assessment in one window, the assessment with the latest outcome will be used for the analysis unless a PD has been recorded earlier then PD will be used.

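### In the PFS derivation table, the two rows for patients without a baseline scan use different anchors (second planned versus second performed scan), so some deaths meet both rows and some meet neither

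*SAP*

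**What the plan says.** The protocol (7.3.1, Derivation of PFS) leaves the detailed censoring rules to the SAP, so SAP Table 5.1.2: 1 is the operative rule for the phase II primary endpoint.

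For patients with no baseline radiological assessment the table has two rows:

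- Event, dated at death: "Patient with death on or before the second planned radiological assessment".
- Censored, dated at randomisation: "Patient without death or patient with death after second performed radiological assessment".

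The next block, for patients without post-baseline assessments, uses *planned* in both of its death rows: "Death prior or on the second planned radiological assessment" is an event, and "Death beyond the second planned radiological assessment" is censored at randomisation.

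SAP 5.1.2 also records that imaging became more flexible after protocol amendment 3, but that "it was decided to keep the initial planned schedule for the definition of time windows for censoring rules". SAP 6.7.2 fixes the planned dates: "Due date of scans = (nominal time point * 7) + 1", with day 1 as the date of randomisation in phase II.

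**The concern.** A pair of rows that sorts deaths into event or censored should cover every death once. These two rows can do so only if the second scan performed always falls on the date of the second scan planned. The protocol does not ensure that. It allows scans up to seven days before the due date, unscheduled scans, and a scan at the end-of-treatment visit. Neither document treats the two terms as the same, and neither says which row takes precedence.

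At stake is the primary endpoint of an affected patient. PFS is the outcome date minus the randomisation date plus 1. A death on day 100 gives either an event at 100 days or a censored time of 1 day. In the second case the patient contributes almost nothing to the Cox model. For other patients the table returns no outcome at all.

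**Working it through.** **Inputs**

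- Event row: death on or before the second planned scan (SAP Table 5.1.2: 1).
- Censoring row: death after the second performed scan (same table).
- Scan due date = nominal week x 7 + 1 (SAP 6.7.2).
- Protocol timing of the second scan: "during week 16 (105-112 days after randomisation" (phase II flow chart, tumour assessment footnote).
- Assumption: the first two planned scans are those at weeks 8 and 16, with screening not counted.

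**The plan's own figure**

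Week 16: 16 x 7 + 1 = day 113. The window bounds are midpoints between due dates. The lower bound is (57 + 113)/2 + 1 = 86 and the upper bound is (113 + 169)/2 = 141. SAP Table 6.7.2: 1 states the same values, 113 and 86 to 141.

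**Deaths sorted by both rows** (no baseline scan, no new anti-cancer therapy)

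| Post-baseline scans (day) | Death (day) | Event row: death ≤ 113? | Censoring row: death after second performed scan? | Result as written | Result with *planned* in both rows |
|---|---|---|---|---|---|
| 55 | 90 | yes | no | event | event |
| 50, 90 | 100 | yes | yes | **both** | event |
| 50, 106 | 110 | yes | yes | **both** | event |
| 57, 113 | 150 | no | yes | censored | censored |
| 57 | 150 | no | no | **neither** | censored |

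**Width of the overlap**

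A second scan on day s creates an overlap for deaths from day s + 1 to day 113, which is 113 - s days.

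- Scans on schedule: 105 to 112 days after randomisation is study day 106 to 113. The overlap runs from 113 - 106 = 7 days down to 113 - 113 = 0.
- Off-schedule second scan, with assessments counted once per nominal window as in SAP 6.7.2: all scans on days 1 to 85 count as week 8, so a second assessment needs day 86 or later. The overlap is at most 113 - 86 = 27 days.
- Off-schedule second scan, with every scan counted separately: the overlap can be longer. Scans on days 50 and 80 with death on day 100 would then meet both rows; under window counting they would not. The SAP does not say which count *performed* means.

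The example with scans on days 50 and 90 survives either count, because day 90 lies in the week 16 window. It is also a plausible pattern. The scans are 90 - 50 = 40 days apart, so if treatment stops for a reason other than imaging-based progression, the flow chart's four-week exemption from the end-of-treatment scan does not apply.

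**Width of the gap**

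A patient with neither a baseline nor a post-baseline scan who dies after day 113 is handled by the next block. A patient who starts new anti-cancer therapy before death is handled by the rows for subsequent therapy. What remains is a patient with no baseline scan, exactly one post-baseline scan, death after day 113 and no new therapy.

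**The case against.** The mismatch itself is hard to dispute. The case against concerns its reach and its consequences, and much of that case stands.

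*Few patients.* Entry requires a measurable lesion or a lytic or mixed bone lesion, and screening imaging within 28 days of treatment, so the no-baseline block should be nearly empty. A reader might infer from violation code C1 ("Screening imaging earlier than 28 days to first drug intake") that the SAP expects such patients. It does not: a violation category is not a forecast, and C1 does not say that a patient with an early scan is classed as having no baseline. The block is nevertheless reachable. SAP 6.7.1 requires baseline tumour evaluations to come from scans within 28 days of treatment start, and SAP 6.2 excludes nobody for a C1 violation.

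*Who decides.* In an open-label trial a reader might infer that the ambiguity would be settled by someone who knows the patient's arm. The documents do not support that. Protocol 4.1.2.2 denies those conducting and analysing the trial access to the randomisation schedule. Protocol 4.1.5.1 keeps the trial team blinded to aggregated treatment-level data until database lock. SAP 6.2 and 6.6 place comparable open decisions at a blinded report planning meeting or otherwise before lock. Individual arms may still be inferable, which supports *might* and no more.

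*Intent.* A reader might take the next block as proof that *planned* was meant throughout. It is weak proof: its patients have no performed post-baseline scans, so *planned* is the only anchor available there. The decision in SAP 5.1.2 to keep the planned schedule for the censoring windows is the better evidence.

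*Unevaluable scans.* Scans rated not evaluable count as missed, and a scan without a baseline might be rated that way. Some gap patients could then fall into the no-post-baseline block. That is a reading; the SAP does not state it.

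*Exploratory purpose.* No formal test is planned, and both documents define death from any cause as a PFS event, which gives some guidance for the overlap cases.

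**Conclusion.** The two no-baseline rows are inconsistent as written. Certain deaths are assigned both outcomes and certain others none, within the derivation of the primary endpoint.

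The size is small. The documents give no count of affected patients, and very few are likely. Each overlap case moves the event count by one; against the 90 events planned in protocol 7.6 that is 1/90 = 1.1%. The share would be larger if fewer events were observed by the 25 November 2016 cut-off. Nothing in the documents allows a statement about the hazard ratio, and none is made here. Sample size and event target are untouched.

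The result assumes that the second planned scan is the week 16 scan on day 113, and that a scan rated not evaluable still counts as performed. The point calls for an unambiguous rule. It is not evidence of a biased or unblinded decision. It belongs at the lowest level of priority.

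**What to change.** In the no-baseline censoring row of SAP Table 5.1.2: 1, replace *performed* with *planned*. Every death in the block then falls in exactly one row: day 113 or earlier is an event at death, and later is censored at randomisation. This agrees with the planned schedule retained for the censoring windows. It also removes the questions of how scans are counted and whether an unevaluable scan counts as performed.

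Stating which row takes precedence would also settle the overlap, but would leave the gap open, so the wording change is preferable. A short note that the second planned assessment is week 16, day 113, would complete it.

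The cost is one word in the table, plus the optional note. No data collection, sample size or event target changes. Only the programmed PFS rule for this block needs to be checked against the revised row.

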5.2 SECONDARY ENDPOINTS

5.2.1 Key secondary endpoints

Not applicable.

5.2.2 Other secondary endpoints

5.2.2.1 Phase Ib

There are no secondary endpoints.

5.2.2.2 Phase II

Time to progression (TTP)

TTP is defined as the time from randomisation until tumour progression according to RECIST 1.1.

For patients with 'event' as an outcome for TTP:

- TTP [days] = date of outcome - date of randomisation +1.

For patients with 'censored' as an outcome for TTP:

- TTP (censored) [days] = date of outcome - date of randomisation +1.

Patients without a progression event at the time of the primary analysis will be censored at the time of the last evaluable radiological image. An evaluable radiological image for censoring of time to progression is an image for which an overall response assessment of SD, Non-CR/Non-PD, PR or CR has been assigned. This is used for censoring of patients without progression at end of trial, or censoring prior to missed assessments, or censoring prior to subsequent anti-cancer therapy.

More detailed censoring rules are indicated in Table 5.2.2.2: 1.

Table 5.2.2.2: 1 Derivation rules for Time to Progression

Situation	Outcome (event or censored)	Date of outcome
No baseline radiological assessment	Censored	Date of randomisation (or first treatment administration, in non-randomised trials)
Without post-baseline radiological assessments	Censored	Date of randomisation (or first treatment administration, in non-randomised trials)
With post-baseline radiological assessments BUT no subsequent anti-cancer therapy		
Alive and no tumour progression, no more than one consecutively missed radiological assessments	Censored	Date of last radiological assessment

Proprietary confidential information © 2018 Boehringer Ingelheim International GmbH or one or more of its affiliated companies

Table 5.2.2.2: 1 Derivation rules for Time to Progression (cont.)

Situation	Outcome (event or censored)	Date of outcome
Alive and not progressed, two or more consecutively missed radiological assessments	Censored	Date of last radiological assessment prior to missed radiological assessments
Tumour progression, zero or one missed image prior to progression	Event	Date of radiological assessment of progression
Progression, two or more consecutively missed radiological assessments prior to progression	Censored	Date of last radiological assessment prior to missed assessments
Death but no progression	Censored	Date of last radiological assessment prior to death
With post-baseline radiological assessments AND subsequent anti-cancer therapy		
Subsequent anti-cancer therapy started before progression	Censored	Date of last radiological assessment before subsequent anti-cancer therapy

Objective response (OR)

OR is defined as best overall response of CR or PR, where best overall response is determined according to RECIST 1.1 from randomisation until the earliest of disease progression, death or last evaluable tumour assessment before start of subsequent anti-cancer therapy.

Time to OR

Time to objective response is defined as the time from randomisation until first documented CR or PR.

Time to objective response will only be calculated for patients with an objective response:

- Time to OR [days] = date of first documented CR or PR - date of randomisation + 1.

Duration of OR

Duration of objective response is defined as the time from first documented CR or PR until the earliest of disease progression or death among patients with objective response.

Duration of objective response will only be calculated for patients with an objective response. For patients with disease progression or death:

- Duration of OR [days] = date of outcome – date of first assessment indicating OR + 1.

Proprietary confidential information © 2018 Boehringer Ingelheim International GmbH or one or more of its affiliated companies

For patients without disease progression or death:

- Duration of OR (censored) [days] = date of outcome – date of first assessment indicating objective response + 1

The censoring rules for duration of OR are given in Table 5.2.2.2: 2.

Table 5.2.2.2: 2 Derivation rules for Duration of Objective Response

Situation	Outcome (event or censored)	Date of outcome
No other anti-cancer therapy		
Alive and not progressed, no more than one consecutively missed radiological assessments	Censored	Date of last radiological assessment
Alive and not progressed, two or more consecutively missed radiological assessments	Censored	Date of last radiological assessment prior to missed radiological assessments
Progressed, zero or one missed radiological assessment prior to progression	Event	Date of radiological assessment of progression
Progressed, but two or more consecutively missed radiological assessments prior to progression	Censored	Date of last radiological assessment prior to missed assessments
Death but no progression, zero or one missed radiological assessment prior to death	Event	Date of death
Death without progression, but two or more consecutively missed radiological assessments prior to death	Censored	Date of last radiological assessment prior to missed assessments
Initiation of subsequent anti-cancer therapy		
Subsequent anti-cancer therapy started before progression or death, no more than one consecutively missed radiological assessments prior to start of subsequent anti-cancer therapy	Censored	Date of last radiological assessment before initiation of subsequent anti-cancer therapy

Proprietary confidential information © 2018 Boehringer Ingelheim International GmbH or one or more of its affiliated companies

Only radiological assessments after first assessment indicating objective response will be taken into consideration.

Disease control (DC)

DC is defined as best overall response of CR or PR, or SD \geq 24 weeks, or Non-CR/Non-PD for \geq 24 weeks where best overall response is defined according to RECIST version 1.1 from date of randomisation until the earliest of disease progression, death or last evaluable tumour assessment before start of subsequent anti-cancer therapy (see [Section 5.4.7](#)).

Duration of DC

Duration of DC is defined as the time from randomisation until the earliest of disease progression or death, among patients with DC.

Duration of DC will only be calculated for patients with a DC. For patients with disease progression or death:

- Duration of DC [days] = date of outcome – date of randomisation + 1.

For patients without disease progression or death:

- Duration of DC (censored) [days] = date of outcome – date of randomisation + 1.

The censoring rules for duration of DC are given in Table 5.2.2.2: 3.

[figure not shown]
Table 5.2.2.2: 3 Derivation rules for Duration of Disease Control

[figure not shown]
Situation	Outcome (event or censored)	Date of outcome
With baseline and post-baseline radiological assessments BUT no other anti-cancer therapy		
Alive and not progressed, no more than one consecutively missed radiological assessments	Censored	Date of last radiological assessment
Alive and not progressed, two or more consecutively missed radiological assessments	Censored	Date of last radiological assessment prior to missed radiological assessments
Progressed, zero or one missed radiological assessment prior to progression	Event	Date of radiological assessment of progression
Progressed, but two or more consecutively missed radiological assessments prior to progression	Censored	Date of last radiological assessment prior to missed assessments
Death but no progression, zero or one missed radiological assessment prior to death	Event	Date of death

[figure not shown]
Proprietary confidential information © 2018 Boehringer Ingelheim International GmbH or one or more of its affiliated companies

Table 5.2.2.2: 3 Derivation rules for Duration of Disease Control (cont.)

Situation	Outcome (event or censored)	Date of outcome
Death without progression, but two or more consecutively missed radiological assessments prior to death	Censored	Date of last radiological assessment prior to missed assessments
Initiation of subsequent anti-cancer therapy		
Subsequent anti-cancer therapy started before progression or death	Censored	Date of last radiological assessment before subsequent anti-cancer therapy
No baseline and/or post-baseline imaging and subsequent anti-cancer therapy started prior to a death	Censored	Date of randomisation (or first treatment administration, in non-randomised trials)

